8. PROTOCOL VIOLATIONS AND DEVIATIONS

Except in the event of a medical emergency or where it is necessary to protect the safety, rights or welfare of the study subject, any changes to the protocol will require written approval of Sebela or designee. Violations or deviations from the Clinical Investigational Plan to protect the health and safety of the subject will be reported to the IRB and as required by local regulations. All protocol violations or deviations will be recorded, tracked and reviewed periodically by Sebela and its designee, according to the process established prior to first patient enrolled. A protocol violation or deviation may be requested in advance of implementation and will be reviewed for approval by Sebela or its designee, or a violation/deviation may be identified after the fact, by the investigator, Sebela, or the monitoring staff. Investigators should ensure all scheduled PK samples are collected without protocol deviations. Investigators will be asked to provide an explanation for the all violations and deviations identified. Sebela, or designee, will be responsible for analyzing deviations and may implement corrective actions as necessary.

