11.3. Analysis Populations

The PK study population will include all randomized subjects whose pre-insertion total serum copper concentrations were within the normal range (49 to 185 $\mu\text{g}/\text{dL}$) [7], had an IUD placed successfully, and completes all scheduled PK sample collections without a protocol deviation or AEs that significantly impact the planned PK analyses.

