6. PHARMACOKINETIC POPULATION

6.1 Pharmacokinetic Population

The PK study population is defined as all randomized subjects for which all pre-insertion total serum copper concentrations were within the normal range (49 to 184 µg/dL), had an IUD placed successfully, and completed all scheduled PK sample collections without a protocol deviation or AEs that significantly impact the planned PK analyses.

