6.2 Changes to Protocol-Specified Population

The protocol defines the overall PK study population but not the PK concentration and PK parameter populations.

The PK concentration population is defined as all randomized subjects that have an IUD placed successfully and have at least one quantifiable total serum copper concentration post-insertion. Concentration data from this population will be presented in the tables and used in the calculation of summary statistics for plotting purposes.

The PK parameter population is defined as subjects in the PK concentration population with sufficient data to calculate PK parameters (at least 4 quantifiable total serum copper concentrations and no protocol deviations that have a material impact on the PK). This population will be included in the NCA and individual copper concentration versus time figures.

Any other changes to protocol-specified population due to protocol deviations or other factors that may impact PK will be detailed in the final PK report.

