Cmean	Mean total serum copper concentration of samples collected after Day 1 (Days 3-57)
AUC0-56 days	Area under the concentration time curve, from time 0 (study Day 1) to the last measurable non-zero concentration up to 56 days (study Day 57), calculated by the linear trapezoidal method

Note that the abbreviations and definitions listed above may differ slightly from the protocol in the phrasing; however, the equations and methods used to generate these parameters do not differ from the protocol.

Additional PK parameters may be calculated, as necessary, to fully characterize the PK profiles of uncorrected and baseline-corrected serum copper and will be defined in the final PK report.

No PK parameters will be calculated for subjects with fewer than 4 quantifiable total serum copper (uncorrected) concentrations following imputation of concentrations below the limit of quantification (BLQ) (see Section 8.4). Baseline-corrected copper PK parameters will be calculated for all subjects regardless of the number of non-zero concentrations.

All subjects in the PK parameter population (see Section 6.2) will be included in the descriptive statistics for the PK parameters. PK parameters will be listed for each subject by treatment, and the following descriptive statistics will be provided: N (number of subjects with non-missing data), arithmetic mean, SD, CV%, median, minimum, and maximum. Geometric mean and geometric CV% will be calculated for continuous PK parameters. Tmax will be presented as N, median, minimum, and maximum. Parameters that are equal to zero will be reported as “missing”.

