8.4 Imputation of BLQ Values

For the calculation of mean concentrations and generation of mean concentration versus time profiles, all BLQ values will be set to zero, except when an individual BLQ falls between two quantifiable values, in which case it will be treated as missing data.

For the PK analysis and individual concentration versus time plots, a concentration that is BLQ is assigned a value of zero if it occurs in a profile before the first measurable concentration. If a BLQ value occurs after a measurable concentration in a profile and is followed by a value above the lower limit of quantification, then the BLQ is treated as missing data. If a BLQ value occurs at the end of the collection interval (after the last quantifiable concentration), it is treated as missing data. If 2 BLQ values occur in succession after Cmax, the profile is deemed to have terminated at the first BLQ value, and any subsequent concentrations are omitted from PK calculations.

In circumstances where alternative approaches to handling BLQ data are necessary, the relevant modifications will be appropriately documented in the clinical study report or final PK report.

Baseline-corrected serum copper concentrations that are less than or equal to zero will be treated as zero for the calculation of summary statistics and in the noncompartmental analysis.

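### AUC0-56 is defined to stop at the last measurable non-zero sample, so baseline-corrected areas end early even in fully sampled subjects; a fixed 0 to 56.0 day interval and a named ANCOVA population would settle it (minor)

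*SAP*

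**What the plan says.** **End of the area.** PK SAP Table 8-2 (section 8.1) takes AUC0-56 from time 0 "to the last measurable non-zero concentration up to 56 days (study Day 57), calculated by the linear trapezoidal method". Protocol 11.4.1 has the same definition. The protocol's List of Abbreviations, and the safety SAP's abbreviation list and section 2.1, give an area from study Day 1 to day 56 (study Day 57), without the stop at the last non-zero value.

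**Zeros and missing values.** PK SAP 8.4: "Baseline-corrected serum copper concentrations that are less than or equal to zero will be treated as zero", both in summaries and in the noncompartmental analysis. PK SAP 8.1 adds: "Baseline-corrected copper PK parameters will be calculated for all subjects regardless of the number of non-zero concentrations". Sections 8.5 and 8.6 plan no imputation and no data exclusions, so an area that stops short stays short.

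**Sampling.** The last two visits of the comparison phase are Day 29 (window 1 day either side) and Day 57 (3 days either side). The final analysis uses actual times.

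**Populations.** The PK population in PK SAP 6.1 is limited to subjects who "completed all scheduled PK sample collections without a protocol deviation or AEs that significantly impact the planned PK analyses"; protocol 11.3 matches it. The PK parameter population in 6.2 asks only for "at least 4 quantifiable total serum copper concentrations and no protocol deviations that have a material impact on the PK". It feeds the noncompartmental analysis and the parameter summaries. PK SAP 8.2 and protocol 11.5 describe the ANCOVA of Cmax, Cmean and AUC0-56 and name no population.

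**The concern.** A parameter labelled 0-56 should cover the same interval in every subject. Under the operative definition it need not, for three reasons.

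- **Corrected copper.** A zero is a valid observation (no excess over baseline), yet the definition treats it as the end of the profile. The corrected area then depends on when the last value above baseline falls, and not only on exposure over 56 days. No choice of population removes this.
- **Uncorrected copper.** Serum copper is endogenous, so the area grows almost in proportion to the time integrated. The Day 57 window therefore enters the primary AUC as noise, and the text does not say how a sample taken after 56.0 days is cut back.
- **Early leavers.** The 6.2 population can include a subject whose last sample is well before Day 57, for example after early removal, when the Exit Visit (protocol 6.1.6 and 6.1.7) takes a final PK sample. Her short area would be tabulated as AUC0-56.

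At stake are the size of a secondary parameter, a little precision on a primary one, and the meaning of the descriptive AUC0-56 tables.

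**Working it through.** **Inputs.** Typical serum copper 110-120 µg/dL (115 used), SD 25, half-width target 22 µg/dL, 12 evaluable and 20 enrolled per group: protocol 11.1. Visit days and windows: protocol 3.1. Baseline is the mean of three pre-insertion values: protocol 11.4.1. Study Day 57 is 56 days after time 0.

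**The plan's own figure.** The 90% CI half-width is t × s × √(2/n). The probability that it is at most 22, given that the interval covers the true difference, is 0.897 at n = 11 and 0.954 at n = 12. So 12 per group and the stated 0.95 are right, and 12/(1 - 0.40) = 20. The sample size is not in question.

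**(a) Corrected AUC, one subject.** Take 0 at time 0, 10 µg/dL from Day 3 to Day 29, and 0 at Day 57.
- As written: 0.5 × 10 × 2 + 10 × 26 = 270 µg·day/dL.
- Through the zero: 270 + 0.5 × 10 × 28 = 410, which is 52% more.

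**(a) Corrected AUC, all subjects, no device effect.** Assume independent normal variation around each subject's level.
- By symmetry, half of subjects have a corrected Day 57 value at or below zero.
- Two corrected values share the same three-sample baseline, so their correlation is (1/3)/(1 + 1/3) = 0.25. The chance that Day 29 is positive and Day 57 is not is 1/4 - arcsin(0.25)/(2π) = 0.21. In these subjects the area stops at Day 29.
- In simulation (200,000 subjects, nominal times), integrating through the zeros raises the group mean by 13% and the median affected subject by about 70%.

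**(a) Effect on the ratio.** With equal arms it is unchanged. With VeraCept at no excess and an assumed ParaGard excess of 5, 10 or 20 µg/dL to Day 57, or 10 or 20 to Day 29 only, the as-written ratio divided by the through-zero ratio ranges from 0.87 (for example 0.104 against 0.119) to 1.08. The log SD of corrected AUC is about 1.30 as written and 1.29 through the zeros. At 12 per arm, without covariate adjustment, the 90% CI factor is exp(1.717 × 1.30 × √(2/12)) = 2.5 either way.

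**(b) Uncorrected AUC, Day 57 window.** At 115 µg/dL, 56 days give 115 × 56 = 6,440 µg·day/dL. A sample at 53 days gives 6,095 (-5.4%). A sample at 59 days gives 6,785 (+5.4%) if the area past day 56 is counted. Simulated ANCOVA half-widths at 12 per arm, as a percentage of the mean and with area past day 56 counted:

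| Reading of SD 25 | As written | Fixed 0-56.0 |
|---|---|---|
| SD of one sample (intraclass correlation 0.5 to 0.9) | 5.6-9.4% | 5.1-9.1% |
| SD of the compared parameter (baseline correlation 0 to 0.7) | 11.2-15.6% | 11.0-15.4% |

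The gain is largest where subjects are most stable, at about 5.5% against 5.0%. There is no bias, because the windows are the same in both arms.

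**(c) Early leavers in the 6.2 tables.** A last sample on Day 29 gives 115 × 28 = 3,220, or 50% of 6,440. Each such subject lowers her arm's mean by 0.5/20 = 2.5% at 20 per arm, or 0.5/12 = 4.2% at 12 per arm.

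**The case against.** **The ANCOVA population can be inferred.** The protocol synopsis defines an evaluable subject as one with all scheduled samples, and protocol 11.1 sizes the 90% CI on 12 of them per group. Protocol 11.3 gives only that population, and PK SAP 8.3 plans no change to the protocol-defined analysis. The 6.2 populations are assigned tables, figures, noncompartmental analysis and descriptive statistics, not inference. If 6.1 is not the ANCOVA set, the PK SAP gives it no use. This stands: 6.1 is the better-supported reading, although 8.2 should say so.

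**A stronger reading is tempting.** A reader might infer that unequal early exit will appear as a copper difference in the primary ANCOVA. If the 6.2 population were used with 20 per arm and no true difference, 2 against 0 subjects truncated at Day 29 would shift the AUC difference by 5.0% of the mean and lower 90% CI coverage to 0.80-0.87. The documents do not support this as a finding. It needs the less likely population, an early exit that the 6.2 deviation filter does not remove, and an imbalance for which the documents give no figure. Protocol 8 also says "Investigators should ensure all scheduled PK samples are collected without protocol deviations", so a missed draw would probably be caught by that filter. The 40% unevaluable allowance cannot supply the counts, because it also covers out-of-range baseline copper and failed placement. One such subject against none leaves coverage at 0.90-0.91, and balanced loss gives no bias.

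**There is a rule.** Stopping at the last measurable value, with no imputation, is a rule and not an omission. That is fair. The complaint is that this rule does not deliver the interval in the label.

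**The corrected parameter is secondary.** The plan expects no additional systemic copper, so the ratio should hardly move. This also stands. The 52% and 70% figures are within-subject changes, not treatment effects.

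**Conclusion.** The point holds and is minor. As written, AUC0-56 is not a 0 to 56 day area.

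- **Corrected AUC:** with no device effect, about half of subjects stop early despite a Day 57 sample, and the group mean is understated (+13% when integrated through the zeros). This assumes independent normal variation. The ratio moves by -13% to +8% only if ParaGard raises copper by an assumed 5-20 µg/dL, and the CI is far wider than that.
- **Uncorrected AUC:** the window adds noise only. An area can be up to 5.4% short, or up to 5.4% long if time past day 56 counts; the wording of the definition leaves the latter open. The half-width grows slightly.
- **Population:** under the 6.1 reading, truncation does not bias the ANCOVA. What remains is that 8.2 does not say so, and that the 6.2 descriptive tables can carry shortened areas (50% for a Day 29 exit) under the AUC0-56 label.

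A reader should not conclude that the primary comparison is biased, or that the plan leaves a free choice of population after the data are seen.

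**What to change.** 1. **Interval.** In PK SAP Table 8-2 and protocol 11.4.1, define AUC0-56 as the partial area from 0 to 56.0 days at actual times. Interpolate to 56.0 whenever a sample at or after 56.0 exists, including a late Day 57 visit with the device still in place. Carry an in-window Day 57 sample taken before 56.0 forward to 56.0. Otherwise set AUC0-56 to missing.
2. **Corrected copper.** State that values set to zero stay as data points and that the area runs through them to 56.0 days.
3. **Population.** State in 8.2 that the ANCOVA uses the PK population of 6.1 and protocol 11.3. In the 6.2 summaries, do not label a truncated area AUC0-56. A time-normalised area (area to the last sample divided by its duration) in the 6.2 population may serve as a sensitivity analysis.

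The cost is a few sentences. Partial areas are a routine setting in the software, and no new data are needed. The downside is that up to 3 days of area (3/56 = 5.4%) is extended rather than observed in subjects seen early in the window. The time-normalised area can also overstate exposure in early leavers if copper is highest early, so it should stay a sensitivity analysis.

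The trapezoid rule also differs between the protocol synopsis (linear up/log down) and protocol 11.4.1 and Table 8-2 (linear). That is a separate point to reconcile.

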8.2 Statistical Analyses

For the primary analysis, an analysis of covariance (ANCOVA) model with fixed effects for treatment and Day 1 pre-insertion concentration as a continuous effect will be used to analyze the uncorrected PK parameters Cmax, Cmean, and AUC0-56 days. As such, a point estimate of the difference between treatments and a 90% confidence interval (CI) of the difference will be provided.

For the secondary analysis, an ANCOVA model with fixed effects for treatment and natural log (ln) transformed Day 1 pre-insertion concentration as a continuous effect will be used to analyze the ln transformed corrected PK parameters Cmax, Cmean, and AUC0-56 days. For each treatment comparison, a point estimate and 90% CIs will be provided for the geometric least squares mean ratio upon back-transformation.

In addition, for each PK assessment day, the number and percentage of PK assessments within the total serum copper normal range (49 to 184 $\mu\text{g}/\text{dL}$) will be assessed for each treatment. A shift table will also be provided for each of the PK days post Day 1 relative to the normal range.

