11.1. Determination of Sample Size

The assumption is that there is no additional systemic exposure of copper when using the IUD. The primary analysis will use uncorrected total serum copper parameters (Cmax, Cmean, AUC0-56 days). A secondary analysis will be conducted using baseline-corrected total serum copper parameters (Cmax, Cmean, AUC0-56 days).

For the analysis using Cmax and Cmean, no formal hypothesis testing is being done. As such, a precision approach will be taken with boundaries chosen to reflect typical BE boundaries in the ln scale (plus or minus 22%). Assuming a normal range of 49 to 184 $\mu\text{g/dL}$, an estimate of the normal (mean) value could be close to 110-120 $\mu\text{g/dL}$. A comparable boundary would be plus or minus 22. This estimated mean with the added half-width still falls well within the normal range.

For the analysis using AUC0-56 days, no formal hypothesis testing is being done. As such, a precision approach will be taken with boundaries chosen to reflect typical BE boundaries in the ln scale (plus or minus 22%). AUC values will be ln transformed.

For a two-sided 90% confidence interval for a two-sample normal mean difference, assuming a common standard deviation of 25, a sample size of 12 per group is required to obtain a half-width of at most 22 $\mu\text{g/dL}$ with a conditional probability of at least 0.90 given that the interval contains the true mean difference. The actual probability is 0.95.

Assuming a maximum unevaluable rate of 40%, up to 20 subjects will be enrolled in each group. Replacement subjects may be enrolled, as needed, to ensure that at least 24 evaluable subjects complete the study

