11.2. Randomization

Subjects will be randomized to a treatment group (VeraCept or ParaGard). The study will be conducted at one or two study sites. Participants will be randomly allocated in a 1:1 ratio either to VeraCept or ParaGard. The randomization will be stratified by site, if needed, but centrally managed until 40 subjects have been randomized.

Once the screening assessments are performed, data have been reviewed by an investigator and the subject is considered to be eligible, the investigator or site designee will enroll the subject, assign the subject's enrollment number and determine the treatment group. The subject's number and treatment group will be determined by the sponsor provided randomization schedule. The site will assign the next consecutive subject number and corresponding treatment group. The randomization will occur on the day of first drug placement attempt. If a subject has failed two drug placement attempts, she will be withdrawn from study. Subjects will be blinded to the treatment they receive.

Subjects who drop out of the study may be replaced as agreed by the Principal Investigator and the Sponsor.

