Subjects will be randomized to a treatment group (VeraCept or ParaGard). The study will be conducted at one or more study sites. Participants will be randomly allocated in a 1:1 ratio, either to VeraCept or ParaGard. The randomization will be stratified by site, if needed, but centrally managed until 40 subjects have been randomized.

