5. PHARMACOKINETIC SAMPLE COLLECTION

5.1 Blood Collection and Sample Processing

Two blood samples for PK analysis will be collected within 28 days from Day 1, and at least 24 hours apart within this screening period (can be performed on Screening and Day 1 visits prior to IUD insertion) to establish baseline copper concentrations, on Day 1 prior to IUD insertion, on Day 3, approximately 48 hours after insertion, and on Days 8, 15, 22, 29, and 57 at approximately the same time of day as the prior PK collections. Following the PK collections on Day 57, the PK samples for Months 6, 12, 18, 24, 30, 36, and 48 will be collected within 30 days of the planned collection day. Approximately 3-5 mL of whole blood will be collected for each blood draw. The total volume collected from each subject for all PK samples will be approximately 20 mL.

Blood samples will be collected in containers appropriate for serum collection, such as a “red topped” tube, which does not contain an anticoagulant.

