8. PART B – FINAL PHARMACOKINETIC AND STATISTICAL ANALYSES DURING TREATMENT COMPARISON PHASE

8.1 Noncompartmental Pharmacokinetic Analysis and Descriptive Statistics

All final PK analysis and reporting for the Treatment Comparison and Extension Phases will be performed according to applicable Nuventra standard operating procedures and protocol specifications. PK parameters will be calculated using NCA implemented within a validated installation of Phoenix® WinNonlin® using actual dosing and sampling times. Programming of tables, figures, and listings will be performed using verified templated R code run in validated R Software and RStudio environments. Additional information on the software to be utilized in this study can be found in [Table 8-1](#). The actual version of the software will be included in the final PK report. Additional software may be used, if necessary. All software used will be documented in the final PK report.

Table 8-1. Software List

Software	Use	Version	Company
Phoenix WinNonlin	NCA	V 8.1 or later (Validated as per VAL.001.04)	Certara (Princeton, NJ)
R Software	Input file generation	V 3.4.0 or later (custom code)	R Foundation for Statistical Computing (Vienna, Austria)
	TLFs	V 3.4.0 or later (Validated as per VAL.002.07)	
RStudio	TLFs	V 1.0.143 or later (Validated as per VAL.002.07)	RStudio (Boston, MA)
SAS	Biostatistics	SAS 9.4 or later	SAS Institute, Inc. (Cary, NC)

PK blood samples will be analyzed for total serum copper concentrations using validated bioanalytical methods. The mean of the two screening baseline values and the Day 1 pre-dose concentration will be used for baseline correction.

Descriptive statistics to summarize observed and baseline-corrected serum concentrations include: N (number of non-missing data), Mean (arithmetic mean), standard deviation (SD), arithmetic percent coefficient of variation (CV%), minimum, median, and maximum.

Summaries of plasma concentration data will include data for all subjects in the PK concentration population (see Section 6.2).

PK parameters for uncorrected and baseline-corrected serum copper will be calculated as described in [Table 8-2](#).

Table 8-2. Pharmacokinetic Parameters

Parameter	Description
Data from Treatment Comparison Phase	
Cmax	Maximum observed concentration, observed by inspection of individual study participant serum concentration-time plots
Tmax	Time of maximum observed concentration, obtained directly from the observed concentration-time data

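### The primary ANCOVA adjusts for Day 1 copper alone, leaving out screening copper already collected and giving no rule for site if randomisation was stratified by it; only the width of the primary interval is at stake

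*SAP*

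**What the plan says.** Protocol 11.5 and PK SAP 8.2 give the same primary model for uncorrected Cmax, Cmean and AUC0-56: an ANCOVA with "fixed effects for treatment and Day 1 pre-insertion concentration as a continuous effect will be used to analyze the uncorrected PK parameters", reported as a treatment difference with a 90% CI. PK SAP 8.3 plans no departure from it.

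Screening copper is used elsewhere. For the baseline-corrected parameters, PK SAP 8.1 states: "The mean of the two screening baseline values and the Day 1 pre-dose concentration will be used for baseline correction". How many screening draws are separate from Day 1 is unclear. Protocol 6.2.1 describes two during screening plus one on Day 1, whereas PK SAP 5.1 (like protocol 6.1.1) asks for two samples "at least 24 hours apart within this screening period (can be performed on Screening and Day 1 visits prior to IUD insertion". That leaves two separate draws or only one.

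On site, protocol 11.2 says "The study will be conducted at one or two study sites" and PK SAP 4.1 says "The study will be conducted at one or more study sites". Both allow conditional stratification: "The randomization will be stratified by site, if needed, but centrally managed until 40 subjects have been randomized". Neither mentions site in connection with the model.

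The design has no formal test and is sized on interval width. Protocol 11.1 says that "a sample size of 12 per group is required to obtain a half-width of at most 22" µg/dL, assuming an SD of 25.

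**The concern.** In a trial sized on the width of a 90% CI, with as few as 12 evaluable women per arm, a pre-insertion measurement already in hand is a free source of precision. The plan averages screening and Day 1 copper for the secondary analysis, yet the primary analysis relies on one pre-insertion value, with that day's fluctuation in it.

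Separately, a factor that restricted the randomisation would normally enter the model. If it matters to the outcome and is left out, the interval is too wide for its nominal level. Silence on this leaves a choice open until the data are in hand.

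The secondary ln-scale models are outside this point: screening values already enter them through the correction, and corrected concentrations are floored at zero (PK SAP 8.4).

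**Working it through.** **1. The plan's own figure.** Inputs from protocol 11.1: SD 25, 12 per arm, two-sided 90% CI, half-width at most 22.

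Expected half-width = t(0.95, 22) × 25 × √(2/12) = 1.717 × 25 × 0.408 = 17.5 µg/dL.

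The probability of a half-width of at most 22, given coverage, is 0.9545 at 12 per arm (plan: 0.95) and 0.897 at 11. Enrolment is 12/(1 − 0.40) = 20 per arm. The plan's figures reproduce, and the target is met with no covariate at all.

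**2. AUC0-56.** No SD is given. AUC0-56 is roughly 56 times a time-weighted mean concentration, so assume the CV implied by SD 25 and mean 110-120, that is 0.227 to 0.208. The ln-scale SD, √ln(1 + CV²), is 0.224 to 0.206. The unadjusted half-width is 1.717 × SD × 0.408 = 0.157 to 0.144, against ln(1.25) = 0.223. The chance of meeting that bound exceeds 0.99.

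**3. Adding the separate screening mean, independent within-woman error.** Let ρ (the ICC) be the correlation between any two samples from one woman. It is an assumption. Cmean averages six post-insertion samples, so with single-sample variance 1 its variance is V = (1 + 5ρ)/6. With k pre-insertion samples, R² = ρ² / [V(1 + (k − 1)ρ)/k]; k = 1 is Day 1 only.

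- Day 1 only: t(0.95, 21) × 25 × √(1 − R²) × √(2/12) × √(1 + 1/20)
- Day 1 plus screening mean: t(0.95, 20) × 25 × √(1 − R²) × √(2/12) × √(1 + 2/19)

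At ρ = 0.5, V = 0.583. Day 1 only has R² = 0.429 and half-width 1.721 × 25 × 0.756 × 0.408 × 1.025 = 13.60. With two separate draws R² = 0.643 and the half-width is 1.725 × 25 × 0.598 × 0.408 × 1.051 = 11.06.

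| ρ | Day 1 only | plus one separate draw | plus two separate draws |
|---|---|---|---|
| 0.3 | 15.93 | 15.12 (5.1% narrower) | 14.27 (10.4%) |
| 0.5 | 13.60 | 12.12 (10.9%) | 11.06 (18.7%) |
| 0.7 | 10.60 | 8.90 (16.0%) | 7.92 (25.3%) |
| 0.9 | 6.14 | 4.89 (20.4%) | 4.27 (30.5%) |

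Simulated ANCOVA fits give the same ratios to within 0.002: 0.894, 0.814, 0.747, 0.695 for two draws and 0.949, 0.889, 0.840, 0.796 for one. For Cmax the simulated gain is 5.8-23.0% (two draws) or 2.5-15.5% (one); for AUC0-56 it is 9.2-28.7% or 4.4-19.3%.

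The table takes 25 as the SD of Cmean, and the saving is 0.8 to 2.7 µg/dL. If 25 is the SD of a single sample, multiply by √V: at ρ = 0.3, 10.29 falls to 9.76 (one draw) or 9.21 (two); at ρ = 0.7 with two draws, 9.18 falls to 6.86. Over both readings the saving is roughly 0.5 to 2.7 µg/dL.

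**4. Adding it, with drift.** Let the within-woman correlation decay as exp(−lag/decay). Simulated Cmean width, ICC 0.3 to 0.7:

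- 7-day decay, draws at days −21 and −7: about 3-14% narrower.
- 7-day decay, draws 1-2 days before insertion: no gain.
- 30-day decay, draws at −21 and −7: ratios about 1.02, 1.01 and 1.00 at ICC 0.3, 0.5 and 0.7. Other draw times also give essentially no gain and at worst about 3% wider.

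The 3% ceiling is the price of a covariate that explains nothing: (1.725/1.721) × √[(1 + 2/19)/(1 + 1/20)] = 1.028.

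**5. Site.** Simulated with two sites, 20 randomised per arm with the same site split in each arm, and 12 per arm evaluable at random. A site term that explains nothing widens the interval by 1.2-1.3% (0.1% if all 20 are evaluable). If site explains 5%, 10% or 20% of residual variance, including it narrows the interval by 1.5%, 4.3% or 9.9%. Omitting it gives coverage of 0.905, 0.907 and 0.917 instead of 0.90. The worst case found for both added terms together was 4.2% wider.

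**The case against.** The strongest reply is that nothing is broken. Day 1 is a defensible covariate, the model is prespecified identically in both documents, the estimate is unbiased under randomisation, and the precision target is met unadjusted. The percentage gains are largest where the interval is already short, so the saving is small against a target of 22. Every gain rests on an assumed correlation, and slow drift alone removes it. The site point is empty if there is one site or no stratification, and the error from omission is conservative. A second correlated covariate at 12 per arm needs a rule for missing values and depends on a draw count that the documents leave unclear.

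Timing may also rule the change out as primary. PK SAP 7.1 plans interim PK parameters and Section 11 outputs once about 20 women complete Day 57. PK SAP 11.1.1 refers to a previous Day 57 table of copper shifts by treatment group, and 11.3 to previous Day 57 copper listings by treatment. On the other side, 7.1 plans no statistical analyses at the interim, so the documents do not settle whether comparative results were seen.

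All of this stands as a limit on importance and on how the change may be used. It does not answer two things: a trial judged on interval width leaves collected baseline data out of its primary model, and the role of a possible stratification factor is undefined.

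**Conclusion.** The point holds as an optional improvement, and no conclusion of the trial is at risk. The possible gain in Cmean width is about 10-30% (two separate draws) or 5-20% (one) if within-woman error is independent and the ICC is 0.3 to 0.9. It is about 3-14% with a 7-day decay and draws at days −21 and −7, and essentially nil with a 30-day decay whenever the draws are taken. The loss is bounded at about 3% for the covariate and about 4% for both terms.

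Three stronger readings are tempting, and the documents do not support them.

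- A reader might infer that the primary estimate is biased. Leaving a baseline value or site out of a linear model under 1:1 randomisation costs width only.
- A reader might infer that AUC0-56 precision is in doubt because no SD is stated. With the CV implied by the plan's SD and mean, its bound is met comfortably.
- A reader might take the gain as assured unless screening falls just before insertion. Slow drift removes it at any draw time, and the documents give no correlation to decide the matter.

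**What to change.** In protocol 11.5 and PK SAP 8.2, for the primary uncorrected models only:

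1. State that site is a fixed effect if randomisation was stratified by site. This is worth doing even if the second item is declined. It costs one degree of freedom per extra site, and about 1% in width with two sites if site explains nothing.
2. Keep Day 1 and add, as a second covariate, the mean of the screening concentrations drawn separately from Day 1. First settle how many such draws there are. Give a rule that keeps a woman without one in the model: the PK parameter population requires "at least 4 quantifiable total serum copper concentrations and no protocol deviations that have a material impact on the PK", not a screening value, so a complete-case fit would drop her. Retain the Day 1-only model as a sensitivity analysis.
3. Have the sponsor state whether Day 57 results by treatment have been seen. If they have, keep Day 1 only as primary and report the two-covariate model as a labelled sensitivity analysis.

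The cost is protocol and SAP wording, with no extra samples.
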